5.1 Dose Modifications for Hematologic Toxicity

Patients must meet hematologic criteria for study entry and at the start of each treatment cycle.

5.1.1 Dose-limiting neutropenia

Patients who experience neutropenia that causes a delay of \geq 14 days between treatment cycles in the absence of other toxicity requiring dose modification should have the temozolomide dose reduced by 25% for subsequent cycles (see dose reduction nomogram in [Appendix VII](#)). If patient experiences neutropenia that causes a delay of \geq 14 days between treatment cycles after this dose reduction, protocol therapy should be discontinued.

5.1.2 Dose-limiting thrombocytopenia

For patients who experience thrombocytopenia that causes a delay of \geq 14 days between treatment cycles with or without other hematologic toxicities, the dose of temozolomide should be reduced by 25% for subsequent cycles (see dose reduction nomogram in [Appendix VII](#)). If patient experiences thrombocytopenia that causes a delay of \geq 14 days between treatment cycles after this dose reduction, protocol therapy should be discontinued.

5.1.3 Delayed recovery of platelets and neutrophils

Patients who do not meet criteria to start the next treatment cycle (see [Section 4.5.1](#) or [4.7.1](#)) 21 days after the planned subsequent cycle start date (i.e. there is a \geq 3 week delay in start of next cycle) must be removed from protocol therapy.

5.2 Dose Modifications for Non-hematologic Toxicity

Patients who have experienced non-hematologic toxicity should receive subsequent doses of study medications as described in the following sections.

NOTE: If eflornithine is stopped for any reason and then resumed at same or lower dose, at least 5 days of the resumed/decreased dose of eflornithine should be given prior to starting Day 1 of the next cycle of chemotherapy.

5.2.1 Dose modifications for diarrhea

See [Appendix V](#) for patient/family instructions for supportive care measures for patients who develop therapy-associated diarrhea. Also included are specific instructions for loperamide dosing.

- If Grade 4 therapy-associated diarrhea is experienced by a patient with no evidence of infectious etiology and despite maximal use of anti-diarrheal medications and appropriate use of prophylactic antibiotics, the dose of irinotecan should be reduced by 25% for subsequent cycles (i.e. irinotecan dose 37.5 mg/m^2).
- If diarrhea persists despite maximal use of anti-diarrheal medications and appropriate use of prophylactic antibiotics for Grade 3 diarrhea > 7 days and Grade 4 diarrhea > 3 days after the completion of irinotecan, hold the eflornithine (DFMO) until diarrhea resolves to Grade 1. Then restart at prior dose.
- If Grade 4 therapy-associated diarrhea recurs without an infectious etiology despite reducing the dose of irinotecan by 25%, the dinutuximab dose (Arm A) or both the dinutuximab and eflornithine doses (Arm B) should also be decreased by 25% for subsequent cycles (i.e. dinutuximab dose $13.13 \text{ mg/m}^2/\text{day}$ and eflornithine dose $5 \text{ g/m}^2/\text{day}$ divided TID).
- If Grade 4 diarrhea recurs despite maximal use of anti-diarrheals, prophylactic antibiotics, and the dose reductions, the patient should come off protocol therapy.

5.2.2 Dose modifications for nausea and vomiting

- For patients with Grade 4 regimen-related nausea and vomiting and for patients with Grade 3 regimen-related nausea and vomiting > 7 days in duration who did not receive appropriate anti-emetic therapy, adjustments in the anti-emetic regimen should be made during the next cycle of therapy.
- If severe (Grade 4 or Grade 3 > 7 days) regimen-related nausea and vomiting recurs despite optimized anti-emetic usage, doses of irinotecan and temozolomide should both be reduced by 25% for subsequent cycles (i.e. irinotecan dose 37.5 mg/m^2 ; for temozolomide see dose reduction nomogram in [Appendix VII](#)).
- If severe regimen-related nausea and vomiting recurs despite the dose reduction, the patient should come off protocol therapy.

5.2.3 Dose modifications for dehydration

- If dehydration is related to diarrhea or nausea/vomiting, the guidance in

Section 5.2.1 or 5.2.2 should be followed.

- If regimen-related \geq Grade 3 dehydration persists for > 3 days in the absence of significant diarrhea or nausea/vomiting, doses of irinotecan and temozolomide should both be reduced by 25% for subsequent cycles (i.e. irinotecan dose is 37.5 mg/m^2 ; for temozolomide see dose reduction nomogram in [Appendix VII](#)).
- If \geq Grade 3 regimen-related dehydration recurs and persists for > 3 days despite the dose reduction, the patient should come off protocol therapy.

5.2.4 Dose modifications for elevations in ALT, AST, or GGT

- If elevations in ALT, AST or GGT occur such that values are $> 20x$ ULN for any duration of time OR $> 10x$ ULN but $< 20x$ ULN and persisting for > 7 days, the dose of dinutuximab should be reduced by 25% for subsequent cycles (i.e. dinutuximab dose 13.13 mg/m^2). For the purposes of this trial the ULN for ALT is defined as 45 U/L; institutional ULN values for AST and GGT should be used.
- If elevations of this magnitude involving same liver enzyme(s) recur despite the first dose reduction, the dose of temozolomide (Arm A) or eflornithine and temozolomide (Arm B) should be reduced by 25% for subsequent cycles (i.e. for temozolomide see dose reduction nomogram in [Appendix VII](#); eflornithine dose 5 g/m^2). If the dose limiting elevations of the same liver enzyme(s) recur despite the temozolomide/eflornithine dose reduction, the patient should come off protocol therapy.
- An elevation in ALT that causes a delay of ≥ 14 days between treatment cycles will also require a 25% reduction in the dose of dinutuximab for all subsequent cycles (i.e. dinutuximab dose 13.13 mg/m^2). If a delay of ≥ 14 days between treatment cycles recurs due to elevation in ALT despite the dose reduction, the patient should come off protocol therapy.

5.2.5 Dinutuximab specific dose modifications and toxicity management recommendations

5.2.5.1 Treatment of dinutuximab-induced hypotension (without evidence of allergic reaction)

- a. If hypotension is severe and accompanied by poor perfusion, end organ dysfunction, or acidemia – Pediatric Advanced Life Support (PALS) guidelines should be followed and dinutuximab infusion should be discontinued.
- b. In the absence of poor perfusion, end organ dysfunction or acidemia, moderate hypotension is defined as:
 - i. symptomatic decreases in blood pressure (BP) and/or
 - ii. Systolic BP $< 5^{\text{th}}$ percentile based on age and height and baseline BPs OR
 - iii. Systolic or diastolic BP decreased by $> 20\%$ below baseline
- c. For patients with moderate hypotension in the absence of poor perfusion, end organ dysfunction, or acidemia:
 - i. Immediately hold dinutuximab
 - ii. Give normal saline bolus (20 mL/kg as rapidly as possible)
 - iii. Stop or adjust doses of narcotics and sedating H1 blockers

- iv. Consider use of Trendelenberg position
- d. If hypotension persists after the above measures have been taken:
 - i. Reassess perfusion and end organ function
 - ii. Follow PALS algorithm if indicated
 - iii. Repeat NS bolus OR
 - iv. Consider use of albumin if albumin < 3 gm/dL
 - v. Consider use of PRBCs if Hb < 10 gm/dL
 - vi. Consider use of platelets if count <50,000/ μ L
 - vii. Consider transfer to intensive care setting
- e. If hypotension persists following 2 volume boluses, give an additional bolus and prepare to administer pressors
 - i. Epinephrine or norepinephrine is preferred over dopamine if possible
- f. Resumption of dinutuximab
 - i. For patients whose hypotension resolves promptly and completely with limited volume resuscitation (\leq 40 mL/kg) and without requirement for pressor support, dinutuximab may be restarted at 50% of the previous infusion rate. The dinutuximab may be restarted on same day if it is possible to do so within 20 hours of the start of the day's infusion. If blood pressures are stable for 2 hours, the infusion may be given at full rate for that day and subsequent days. If the patient again experiences hypotension requiring multiple volume boluses (e.g. $>$ 40 mL/kg) when dinutuximab is given at full rate but tolerates the 50% infusion rate, the remaining days' doses of dinutuximab should be given at the 50% rate of infusion. If $>$ 20 hours have elapsed since the start of the infusion, restart dinutuximab the following day.
 - If blood pressures are stable for 2 hours after resumption of dinutuximab at the reduced rate, the remainder of the antibody infusion may be given at the full rate
 - If hypotension recurs at the reduced rate, the measures above should again be taken and no further dinutuximab should be given that day. The antibody infusion may be restarted the following day after ensuring that the patient is volume replete. The antibody rate upon resumption of treatment should be 50% of the initial rate. If blood pressures are stable for 2 hours, the infusion may be given at full rate for that day and subsequent days. If the patient's blood pressures are only stable at the 50% rate and not at full rate, the remaining days' doses of dinutuximab should be given at the 50% rate of infusion.
 - ii. For patients who require multiple volume boluses for hemodynamic stabilization, dinutuximab should be resumed the following day at 50% of the initial infusion rate.
 - If blood pressures are stable for 2 hours after resumption of dinutuximab at the reduced rate, the remainder of the antibody infusion may be given at the full rate

- If hypotension recurs at the reduced rate, the measures above should again be taken and no further dinutuximab should be given that day. The antibody infusion may be restarted the following day after ensuring that the patient is volume replete. The antibody rate upon resumption of treatment should be 50% of the initial rate. If blood pressures are stable for 2 hours, the infusion may be given at full rate for that day and subsequent days. If the patient's blood pressures are only stable at the 50% rate and not at full rate, the remaining days' doses of dinutuximab should be given at the 50% rate of infusion.
- iii. For patients who require pressors for treatment of hypotension, if blood pressure is stable off pressors for at least 6 hours, administration of dinutuximab may be resumed at 50% of the initial infusion rate on the day following the hypotensive episode. Care should be taken to ensure that the patient is volume replete. Dinutuximab should not be given to patients who continue to require pressor support. Patients who require pressor support for ≥ 24 hours due to treatment-related hypotension despite appropriate volume resuscitation should discontinue protocol therapy. Patients who again require pressor support when dinutuximab is resumed should discontinue protocol therapy.

5.2.5.2 Treatment of Allergic Reactions/Infusion Reactions

- a. Mild allergic reactions/infusion reactions to dinutuximab infusion
 - i. A mild allergic reaction is limited to rash, flushing, urticaria, mild dyspnea – Grade 1 or 2
 - ii. The following recommendations do NOT apply to Grade 3 or 4 allergic reactions, including anaphylaxis
 - iii. Management
 - Decrease rate of dinutuximab to 50% of full rate
 - Perform serial exams at bedside
 - Administer H1 blocker (diphenhydramine, cetirizine recommended)
 - Administer H2 blocker
 - When symptoms resolve, resume original infusion rate
 - If symptoms recur when original rate is resumed, decrease to 50% rate again
 - Infusion must be stopped after 20 hours (whether the full dose of dinutuximab has been administered or not); document total amount of drug given in the 20 hour time period
- b. Moderate to severe allergic reactions/infusion reactions to dinutuximab infusion
 - i. Moderate to severe reactions include any of the following: symptomatic bronchospasm, allergy-related edema/angioedema, hypotension, or anaphylaxis – Grade 3 or 4
 - ii. The following recommendations do NOT apply to Grade 1 or

2 allergic reactions

iii. Management

- **Immediately hold dinutuximab**
- Assess airway, breathing and circulation
- Follow institutional guidelines for rapid response team notification if clinically indicated
- For airway concerns
 - Administer oxygen and albuterol immediately for bronchospasm
 - Administer IV diphenhydramine
 - Administer epinephrine (1:1000 IM recommended) immediately if upper airway involved or if airway issues are accompanied by cardiovascular collapse
 - Administer IV hydrocortisone (1-2 mg/kg) if the patient has frank anaphylaxis with cardiorespiratory collapse OR if ≥ 2 doses of epinephrine are required OR if moderate to severe symptoms recur upon rechallenge with dinutuximab
- For hypotension in the setting of allergic reaction
 - Give normal saline bolus (20 mL/kg as rapidly as possible)
 - Stop or adjust doses of narcotics and sedating H1 blockers
 - Consider use of Trendelenberg position
 - See previous section for management of persistent hypotension
- For patients with mild bronchospasm or angioedema that does not impact breathing, completely resolves without the use of epinephrine and hydrocortisone and for patients whose hypotension resolves following volume bolus, dinutuximab may be resumed at 50% of the previous rate of infusion on the same day as the reaction occurred. If symptomatic angioedema or asymptomatic bronchospasm recurs when the dinutuximab is restarted, discontinue immunotherapy for that day and if symptoms/signs resolve completely that day, resume the next day with additional pre-medication of hydrocortisone 1-2 mg/kg IV. For this rechallenge, the infusion should be given in an ICU setting.
- For patients whose bronchospasm or angioedema requires the use of systemic epinephrine, protocol therapy should be discontinued.
- For patients with bronchospasm or angioedema that does not require systemic epinephrine but whose hypotension requires more extensive volume resuscitation, guidance in [Section 5.2.5.1](#) should be followed.

5.2.5.3 Management of capillary leak syndrome (\geq Grade 3)

- Hold dinutuximab infusion
- Provide oxygen, fluids as needed
- Diuretics should be used with caution and hypotension avoided
- **See [Section 5.2.5.1](#) for management of hypotension, anemia and hypoalbuminemia**
- Do NOT resume dinutuximab therapy if symptoms of severe capillary leak syndrome persist on the same day or subsequent days of a given cycle. Only resume dinutuximab therapy when the capillary leak syndrome resolves or requires less significant intervention (Grade 2 or less).
- If capillary leak resolves, may resume dinutuximab infusion at 50% rate the same day and for subsequent doses during a given cycle. The infusion may be given at the full rate at the start of subsequent cycles
- If mechanical ventilation (any duration) or pressor support for \geq 24 hours is required due to therapy-related capillary leak syndrome, the patient should discontinue protocol therapy

5.2.5.4 Management of renal insufficiency (unrelated to hypotension)

- Consider the possibility of renal hypoperfusion in the context of borderline hypotension; administer volume if appropriate
- If the patient's creatinine is elevated to $\geq 2 \times$ the upper limit of normal for age/gender (see table in [Section 3.2.6.2](#)) and elevation persists despite optimized fluid management, hold dinutuximab
- Modify dosing of concomitant medications that may contribute to or be affected by renal insufficiency
- When urine output returns to normal and creatinine returns to $< 2 \times$ upper limit of normal for age/gender, resume dinutuximab at 50% rate. If renal function normalizes by the following day, dinutuximab may be administered at full rate. If renal function is not sufficiently improved (urine output normal and creatinine $< 2 \times$ ULN for age/gender) by Day 7, no further dinutuximab should be given during that cycle of therapy. If renal function has normalized by the planned start date for the next cycle, retreatment with dinutuximab is permitted

5.2.5.5 Management of hyponatremia (\geq Grade 3; $\text{Na} < 130 \text{ mEq/L}$ and symptomatic or $120-124 \text{ mEq/L}$ regardless of symptoms)

- Change hypotonic fluids to isotonic fluids as compatibilities permit
- Avoid administration of oral free water
- Correct fluid losses due to diarrhea
- 3% saline is only indicated in the following settings:
 - hyponatremia leading to seizure
 - drop in sodium level > 10 points in 6 hours or less
 - sodium level $< 117 \text{ mEq/L}$
- If Grade 4 hyponatremia persists despite optimal fluid management, discontinue dinutuximab for the remainder of the cycle. Sodium should be monitored closely during the next cycle of therapy. If

hyponatremia improves to Grade 2 or better, or baseline, empiric dose reduction is not required at the start of the next cycle of therapy, though dinutuximab would again be discontinued if Grade 4 hyponatremia were to persist despite optimal fluid management. In such cases, patient should discontinue protocol therapy.

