needed for the full course must be dispensed at one time. See [Section 6.5](#) for additional details and examples.

Irinotecan: IV over 90 minutes daily

Days: 1-5

Dose: 50 mg/m²/dose (regardless of BSA)

Note: Irinotecan should be administered at least 1 hour after the temozolomide has been given.

Higher incidence of cholinergic symptoms has been reported with more rapid infusion rates.

See the Parenteral Chemotherapy Administration Guidelines (CAG) for special precautions, suggestions for patient monitoring, and hydration on the COG website at:

https://www.cogmembers.org/_files/disc/Pharmacy/ChemoAdminGuidelines.pdf

Dinutuximab: IV over 10 hours* daily

Days: 2-5

Dose: 17.5 mg/m²/dose

Note: Due to the increased risk of capillary leak and respiratory compromise with dinutuximab administration, patients should not have dyspnea at rest or an oxygen requirement when starting the first dose of dinutuximab. **Before starting dinutuximab**, please obtain a copy of management recommendations for anaphylaxis and hypotension available in [Appendix XI](#) and the training module on the COG website. It is recommended that these be available on the inpatient unit to facilitate treatment decisions should these symptoms occur.

Refer to [Section 4.4.4](#) for premedication and supportive care for the prevention of anticipated toxicities associated with dinutuximab, and for monitoring during the dinutuximab infusion. Additional information can be found in [Appendix XI](#).

Prior to dinutuximab administration (morning start recommended), administer IV bolus of normal saline (10-20 mL/kg) over 1 hour. Bolus should be given concurrently with irinotecan infusion. On Day 2-5, start dinutuximab immediately following the completion of normal saline bolus and irinotecan infusion. Dinutuximab dose should start at 0.88 mg/m²/hour x 0.5 hour, then gradually increase to 1.75 mg/m²/hour for the remainder of the dose, if tolerated.

*The infusion duration may be extended up to 20 hours for anticipated toxicities (hypotension, tachypnea, etc.), not responding to other supportive measures, and the duration used should be recorded. In the setting of dose reductions described in [Section 5.0](#), the infusion must be no longer than 20 hours, even if the full dose of dinutuximab antibody has not been delivered. Antibody administration should not be given beyond the specified schedule regardless of whether doses were modified or held per guidelines in [Section 5.0](#).

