Please note the maximum infusion time from initiation of dinutuximab is 20 hours even if the total dose has not been administered in that timeframe. The total dose given in 20 hours should be recorded.

Sargramostim: Subcutaneous injection (preferred) or IV over 2 hours daily

Days: 6 through 12

Dose: 250 mcg/m²/dose

Start sargramostim on Day 6 any time after the completion of Day 5 dinutuximab.

The standard route of administration is subcutaneous; in extenuating circumstances, IV administration over 2 hours is permitted. The reason for IV administration of this agent must be documented.

Sargramostim dose will be held if the total white cell count is > 50,000/ μ L. This is not a toxicity of sargramostim but rather a possible outcome related to its use. The sargramostim will be held until the total white cell count is less than 20,000/ μ L and then sargramostim will be resumed at 50% dose for the remainder of that cycle. Full dose sargramostim will be used for subsequent sargramostim cycles.

See [Section 5.0 for Dose Modifications based on Toxicities.](#)

4.4.4 Premedication and Supportive Care recommended for the prevention of anticipated toxicities associated with dinutuximab

Neuropathic pain, allergic reactions, and fever are commonly seen in patients receiving this antibody. Institutional guidelines for supportive care during this portion of therapy should be followed. The use of the following premedications are recommended:

- IV hydration: Administer NS 20 mL/kg IV over 1 hour just prior to each dinutuximab infusion.
- Diphenhydramine 1 mg/kg/dose (maximum 50 mg) IV/PO 20 minutes prior to dinutuximab infusion and scheduled q6h. Hydroxyzine PO (0.5-1.0 mg/kg; max dose 50 mg) may be used instead of diphenhydramine in patients for whom there is a specific indication.
- Ranitidine 1 mg/kg/dose (maximum 50 mg) IV 20 minutes prior to dinutuximab infusion and scheduled q8h or equivalent H2 antagonist e.g. famotidine IV.
- Acetaminophen PO/IV: 15 mg/kg/dose (maximum 1000 mg) 20 minutes prior to each dinutuximab infusion and scheduled q4-6h prn.
- Consider use of cetirizine for patients with a history of allergic reactions

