the COG website. It is recommended that these be available on the inpatient unit to facilitate treatment decisions should these symptoms occur.

Refer to [Section 4.6.4](#) for premedication and supportive care for the prevention of anticipated toxicities associated with dinutuximab, and for monitoring during the dinutuximab infusion. Additional information can be found in [Appendix XI](#).

Prior to dinutuximab administration (morning start recommended), administer IV bolus of normal saline (10-20 mL/kg) over 1 hour. Bolus should be given concurrently with irinotecan infusion. On Day 2-5, start dinutuximab immediately following the completion of normal saline bolus and irinotecan infusion. Dinutuximab dose should start at $0.88 \text{ mg/m}^2/\text{hour} \times 0.5 \text{ hour}$, then gradually increase to $1.75 \text{ mg/m}^2/\text{hour}$ for the remainder of the dose, if tolerated.

*The infusion duration may be extended up to 20 hours for anticipated toxicities (hypotension, tachypnea, etc.), not responding to other supportive measures, and the duration used should be recorded. In the setting of dose reductions described in [Section 5.0](#), the infusion must be no longer than 20 hours, even if the full dose of dinutuximab antibody has not been delivered. Antibody administration should not be given beyond the specified schedule regardless of whether doses were modified or held per guidelines in [Section 5.0](#).

Please note the maximum infusion time from initiation of dinutuximab is 20 hours even if the total dose has not been administered in that timeframe. The total dose given in 20 hours should be recorded.

Sargramostim: Subcutaneous injection (preferred) or IV over 2 hours

Days: 6 through 12

Dose: $250 \text{ mcg/m}^2/\text{dose}$

Start sargramostim on Day 6 any time after the completion of Day 5 dinutuximab.

The standard route of administration is subcutaneous; in extenuating circumstances, IV administration over 2 hours is permitted. The reason for IV administration of this agent must be documented.

Sargramostim dose will be held if the total white cell count is $> 50,000/\mu\text{L}$. This is not a toxicity of sargramostim but rather a possible outcome related to its use. The sargramostim will be held until the total white cell count is less than $20,000/\mu\text{L}$ and then sargramostim will be resumed at 50% dose for the remainder of that cycle. Full dose sargramostim will be used for subsequent sargramostim cycles.

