See the Parenteral Chemotherapy Administration Guidelines (CAG) for special precautions, and suggestions for patient monitoring on the COG website at: https://www.cogmembers.org/_files/disc/Pharmacy/ChemoAdminGuidelines.pdf

Dinutuximab: IV over 10 hours* daily

Days: 2-5

Dose: 17.5 mg/m²/dose

Note: Due to the increased risk of capillary leak and respiratory compromise with dinutuximab administration, patients should not have dyspnea at rest or an oxygen requirement when starting the first dose of dinutuximab. **Before starting dinutuximab**, please obtain a copy of management recommendations for anaphylaxis and hypotension available in [Appendix XI](#) and the training module on

the COG website. It is recommended that these be available on the inpatient unit to facilitate treatment decisions should these symptoms occur.

Refer to [Section 4.7.4](#) for premedication and supportive care for the prevention of anticipated toxicities associated with dinutuximab, and for monitoring during the dinutuximab infusion. Additional information can be found in [Appendix XI](#).

Prior to dinutuximab administration (morning start recommended), administer IV bolus of normal saline (10-20 mL/kg) over 1 hour. Bolus should be given concurrently with irinotecan infusion. On Days 2-5, start dinutuximab immediately following the completion of normal saline bolus and irinotecan infusion. Dinutuximab dose should start at $0.88 \text{ mg/m}^2/\text{hour} \times 0.5 \text{ hour}$, then gradually increase to $1.75 \text{ mg/m}^2/\text{hour}$ for the remainder of the dose, if tolerated.

*The infusion duration may be extended up to 20 hours for anticipated toxicities (hypotension, tachypnea, etc.), not responding to other supportive measures, and the duration used should be recorded. In the setting of dose reductions described in [Section 5.0](#), the infusion must be no longer than 20 hours, even if the full dose of dinutuximab antibody has not been delivered. Antibody administration should not be given beyond the specified schedule regardless of whether doses were modified or held per guidelines in [Section 5.0](#).

Please note the maximum infusion time from initiation of dinutuximab is 20 hours even if the total dose has not been administered in that timeframe. The total dose given in 20 hours should be recorded.

Sargramostim: Subcutaneous injection (preferred) or IV over 2 hours daily
Days: 6 through 12
Dose: $250 \text{ mcg/m}^2/\text{dose}$

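### The renal rule implies held dinutuximab may be resumed on Days 6–7, while the treatment sections bar antibody past the Day 2–5 schedule even after a hold

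*Combined protocol and SAP*

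**What the plan says.** In every cycle of both regimens dinutuximab is a four-day block on Days 2 to 5 (Sections 4.4.3, 4.5.3, 4.6.3 and 4.7.3), with "Dose: 17.5 mg/m²/dose" each day. The therapy delivery maps have dinutuximab entries on those days only.

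Each of the four sections then deals with doses missed for toxicity. Section 4.4.3 reads: "Antibody administration should not be given beyond the specified schedule regardless of whether doses were modified or held per guidelines in" Section 5.0. Section 4.6.3 repeats it for Regimen B ("regardless of whether doses were modified or held per guidelines in" Section 5.0), as do 4.5.3 and 4.7.3. Sargramostim is keyed to the same end point: "Start sargramostim on Day 6 any time after the completion of Day 5 dinutuximab".

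Section 5.2.5.4 holds dinutuximab when creatinine reaches twice the upper limit or more and stays there despite fluid management. On recovery the instruction is to "resume dinutuximab at 50% rate", with full rate allowed if renal function is normal by the next day. If recovery has not occurred "by Day 7, no further dinutuximab should be given during that cycle of therapy". The section gives no last infusion day and does not say whether withheld doses are given later.

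Section 5.2.5.1, on hypotension, has related wording that names no cycle day: "The antibody infusion may be restarted the following day after ensuring that the patient is volume replete".

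**The concern.** A cutoff two days after the last scheduled infusion makes sense only if an infusion can still happen after Day 5. The treatment sections say it cannot, and they say so specifically about doses held under Section 5.0, which contains the renal rule. Two sites that both follow the protocol could therefore treat the same patient in opposite ways.

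At stake is whether a child recovering from renal insufficiency receives further antibody in that cycle, possibly on days when sargramostim is also scheduled (Days 6–12). At trial level, exposure to a backbone drug common to both arms would vary with the section a site happens to read.

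**Working it through.** **Comparing the passages.** Take a patient whose Day 4 dose is withheld for creatinine and who recovers on Day 6.

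- Section 5.2.5.4: recovery came before Day 7, so the stopping clause does not apply and the instruction to resume does.
- Section 4.4.3 (or 4.5.3, 4.6.3, 4.7.3): the scheduled days are over, and the hold does not extend them.

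Nothing in either place says which prevails.

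**Inputs.** Four scheduled days (2–5); 17.5 mg/m² per day; Day 7 cutoff (5.2.5.4); full rate 1.75 mg/m²/hour and maximum infusion time 20 hours (4.4.3). The plan states no figure for the disputed amount, so there is none to reproduce.

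**Cycle total.** 4 × 17.5 = 70 mg/m².

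**Dose count.** Let h be the first day withheld (2 to 5) and r the day of resumption (h + 1 to 7).

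- Under Section 4: (h − 2) + max(0, 6 − r).
- Under 5.2.5.4, assuming one dose a day, withheld doses given late, and Day 7 as the last infusion day: (h − 2) + min(6 − h, 8 − r).

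For the example, h = 4 and r = 6. Section 4 gives 2 + 0 = 2 doses (35 mg/m²); 5.2.5.4 gives 2 + min(2, 2) = 4 doses (70 mg/m²).

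Where recovery falls after Day 5:

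| First day withheld | Resumed | Section 4 | 5.2.5.4 | Disputed doses | mg/m² | Share of cycle |
|---|---|---|---|---|---|---|
| 2 | Day 6 | 0 | 2 | 2 | 35 | 50% |
| 2 | Day 7 | 0 | 1 | 1 | 17.5 | 25% |
| 3 | Day 6 | 1 | 3 | 2 | 35 | 50% |
| 3 | Day 7 | 1 | 2 | 1 | 17.5 | 25% |
| 4 | Day 6 | 2 | 4 | 2 | 35 | 50% |
| 4 | Day 7 | 2 | 3 | 1 | 17.5 | 25% |
| 5 | Day 6 | 3 | 4 | 1 | 17.5 | 25% |
| 5 | Day 7 | 3 | 4 | 1 | 17.5 | 25% |

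The six combinations with recovery by Day 5 also give 1 or 2 disputed doses, but only if doses already missed are made up after Day 5, which the text neither states nor excludes.

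**Sensitivity to the Day 7 assumption.** If Day 7 is only the deadline for recovery and withheld doses are made up without a cap, all four doses are eventually given. The dispute then reaches 4 − 1 = 3 doses (52.5 mg/m², 75%) for a hold from Day 3 with recovery on Day 6 or 7, and 4 − 0 = 4 doses (70 mg/m², 100%) for a hold from Day 2.

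**Does the half rate shrink the amount?** Hardly. Ignoring the slower start, 0.5 × 1.75 × 20 = 17.5 mg/m², so a half-rate infusion can still deliver a full day's dose within the limit.

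**The case against.** The strongest reply is that the conflict is inferred. Section 5.2.5.4 nowhere expressly orders an infusion on Day 6 or 7; it sets a point at which dinutuximab stops. The Section 4 sentence can be read as a precedence rule, and the delivery maps and sargramostim wording agree with it. It is true that dosing on Days 6–7 is implied, not stated. But if Section 4 prevails, the Day 7 clause is left as a live instruction that suggests the opposite, and it still needs correcting.

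A second reply is that the Section 4 sentence concerns only the 20-hour daily limit, because it follows that limit. The limit is already stated separately, before and after, and the sentence speaks of doses held under Section 5.0. That points to dosing days.

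A third is the 72-hour allowance in Section 4.0. It does cover valid clinical reasons, but only minor unavoidable departures, and it excludes what the protocol explicitly prohibits.

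A reader might infer more than the documents support:

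- **A biased response comparison.** The wording is the same in both arms, and no frequency of renal holds is given. Section 2.1's account of notable toxicities in 51 patients on the earlier study of this backbone lists no renal event, which does not prove rarity but offers no support for a material effect.
- **Half a cycle as a ceiling.** That depends on Day 7 being the last infusion day, which the text does not say.
- **The same contradiction in the hypotension and allergic-reaction rules.** Sections 5.2.5.1 and 5.2.5.2 name no cycle day and have no Day 7 clause. Their reach after a Day 5 event merits confirmation, but a contradiction is not shown.
- **A missing creatinine test.** Section 5.2.5.4 itself makes resumption depend on creatinine, and the observation lists tell sites to obtain whatever other studies good care requires.
- **Correlative samples drawn too early.** Sections 14.1.1.1 and 14.1.2.1 and note c of Appendix X require collection after dinutuximab is complete. The window runs to Day 9, so Days 8 and 9 would remain even if antibody ended on Day 7.

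**Conclusion.** The inconsistency stands, in operative text and for both regimens. The Section 4 passages and Section 5.2.5.4 cannot both be followed for a patient whose renal function recovers on Day 6 or 7.

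The 25–50% range rests on three assumptions: one dose per day, withheld doses given late, and no infusion after Day 7. Relaxing the last could take the dispute to 75% or 100% of the cycle for holds that begin on Day 3 or Day 2. How many patients would be affected cannot be estimated from the documents.

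This is a matter of consistent treatment of individual patients and even backbone exposure across sites. It is not evidence that the comparison of response rates is biased. No view is taken here on which rule is right.

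**What to change.** Reconcile Section 5.2.5.4 with the corresponding sentence in Sections 4.4.3, 4.5.3, 4.6.3 and 4.7.3, so that all five give the same last permitted dinutuximab day in a cycle. State there whether withheld doses may be given later. Make the sargramostim start wording consistent with the result. Confirm that the provisions in Sections 5.2.5.1 and 5.2.5.2 for resuming a day later are read the same way when the event occurs on Day 5. The study committee must decide which rule applies.

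The cost is protocol wording only: no added patients and no change to the sample size or analysis.
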